5.1 PATIENT SUBJECT ENROLLMENT

The study staff will perform daily screening of hospital admissions based on the study’s inclusion and exclusion criteria listed above. If an inpatient meets criteria, the study staff will directly approach the nurse, physician attending, or physician assistant who is caring for the patient to briefly explain the study and determine an appropriate time to meet with the patient. We will verify the inclusion and exclusion criteria with the treating provider. If permission is granted by the treating provider, the study staff will meet with the patient at bedside, explain the study to the patient, and ask the remaining exclusion criteria to confirm their eligibility. In particular, the study staff will confirm that the patient has a phone and is capable of sending and receiving text messages. Study staff will also ensure that patients are willing to engage network members in the study if assigned to the intervention arm. If the patient is interested in participating in the study, the study staff will then obtain informed consent from the patient using MGB-approved REDCap digital signature consent process, conduct baseline surveys, randomize the patient and, for intervention arm participants, collect contact information for their network members who will be directly contacted and invited to participate. Patients will be stratified according to network size (<5 vs 5 or more) and location of hospitalization (MGH or BWH), and then be randomized using a 1:1 ratio to receive individual hypertension counseling or the social network intervention.

Patients who are eligible for participation in this study and two other IRB approved studies led by [name] ([name], 2020P003739 and 2020P000320) may be approached for participation in both studies within one enrollment visit. Study staff will explain both studies and emphasize that patients can choose to only participate in one of the studies. If interested, patients will be provided consent forms for both studies and will agree to participate in each study separately. Patients will then go through baseline questionnaires for both studies, completing any repeated questionnaires between both studies only once. Participation in the three studies will otherwise be separate.

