6. STUDY PROCEDURES

6.1 Consent/Enrollment and Baseline Visit

The study staff will meet with the eligible patients at bedside, explain the study to the patient, and obtain written informed consent using MGB-approved REDCap digital signature consent process. The consent form will include consent for enrolled participants to receive follow-up outreach after

completion of the trial to participate in an implementation evaluation, to include either a brief survey or a brief qualitative interview. Study staff will then help the patient complete baseline questionnaires consisting of the validated PERSNET social networks questionnaire, stroke information, and the CES-D depression screen. Additional covariates, such as medication use, will be retrieved from the EHR. The PERSNET resulting network map will be used to identify network team members. Participants will then be randomized to either the Social Networks (intervention) arm or the Individual Counseling (control) arm. In the Individual Counseling arm, while the patient's network will be mapped, it will not be acted upon. In the Social Network arm, network members identified will be invited to participate in the study per the enrollment description above (Section 5.2). All patients will be provided with a wide-range blood pressure cuff (Medline MDS4001 blood pressure monitor) and instructions for weekly home monitoring. Patient will be asked to use this cuff to collect a baseline blood pressure measurement at the time of enrollment. A blood pressure measurement will also be collected from the patient's EHR on the day of discharge from the hospital. Finally, patients will be offered several Zoom meeting options and will schedule the first counseling session with study staff based on their availability.

Both this study and protocols 2020P003739 and 2020P000320 ask patients to complete the PERSNET social networks questionnaire. To simplify the enrollment process, patients that have consented to participate in both studies will only be asked to complete these questionnaires once for protocol 2022P000444. Data from these questionnaires will then be shared with protocols 2020P003739 and 2020P000320.

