6.5 Data Collection Schedule

Time point	Individual Counseling Arm	Social Network Arm
Baseline (Week 0)	
Written consentPERSNETDemographics and stroke data (Age, Sex, Stroke severity, Charlston comorbidity index)Blood pressure measure under direct observation	
Written consentPERSNETDemographics and stroke data (Age, Sex, Stroke severity, Charlston comorbidity index)Blood pressure measure under direct observationNetwork members contact info
Session 1 (Week 2 (+/- 7 days))	
BP measure under direct observationFeasibility measures: number of participants, time of session, connection problems.	
BP measure under direct observationFeasibility measures: number of participants, time of session, connection problems.
Session 2 (Week 6 (+/- 7 days))	
BP measure under direct observationFeasibility measures: number of participants, time of session, connection problems.	
BP measure under direct observationFeasibility measures: number of participants, time of session, connection problems.
End line (Week 12 (+/- 7 days))	
BP measure under direct observationPERSNETPROMISFeasibility measures: number of participants, time of session, connection problems.	
BP measure under direct observationPERSNETPROMISCaregiver burden (primary caregiver)Intervention process evaluation (qualitative semi-structured interview)Feasibility measures: number of participants, time of session, connection problems.
Upon completion of study (or after withdrawal)	
Implementation survey or qualitative interview	
Implementation survey or qualitative interview

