9.1 Statistical Hypothesis

The null hypothesis is that rates of systolic blood pressure change at 3 months will be equal in the intervention arm when compared to the control.

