9.2 Power analysis

This pilot trial will be conducted for 12 months. In that time frame, the study team expects 1126 patients to be eligible across Brigham and Women's Hospital, Massachusetts General Hospital and Spaulding Rehabilitation Hospital (85% of all 1325 ischemic stroke patients given broad inclusion criteria). It is expected that ~20% of the patients will agree to participate based on prior experience of recruitment in this population. This creates a pool of 225 or 19 per month. Thus, the study team can feasibly recruit 60 patients within 4-5 months with buffer for unexpected issues.

Assuming a mean blood pressure of 150 +/- 13 points in the individual counselling arm and an alpha of 0.05, this study will need to enroll a total of 54 patients (i.e., 27 per arm) to have 80% power to detect a 10 mm Hg reduction blood pressure from the social network intervention. Therefore, planned enrollment of 60 should be sufficient power for this study to allow for loss to follow-up.

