9.3 Statistical analysis

The primary outcome will be absolute reduction in systolic blood pressure at 3 months. Secondary outcomes will be attainment of a post-stroke hypertension treatment goal of <130/80 and patient-reported physical function (based on the NIH PROMIS physical function sub-scale). These outcomes will be evaluated, for intervention and control patients, on a 10-minute Zoom exit interview with direct observation on video by the study nurse.

Analysis will be conducted using intention-to-treat principles. Evaluation of the primary outcome and physical function secondary outcome will be completed using linear controlling for any differences in baseline variables despite randomization. Logistic regression will be used for attainment of post-stroke hypertension treatment goal of <130/80 controlling for any differences in baseline variables.

For Aim 2, we will assess how a subset of questions in PERSNET predict the set of network members who were engaged in the intervention. We will calculate positive predictive value of the subset questions versus full network survey questions.

10. Monitoring and Quality Assurance

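### Section 9.3 selects the primary model's covariates by observed baseline differences, with no threshold or list, and nothing commits baseline SBP or the stratification factors to the model

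*Combined protocol and SAP*

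**What the plan says.** Section 9.3 takes the absolute reduction in SBP at 3 months as the primary outcome. The analysis of this outcome and of PROMIS physical function "will be completed using linear controlling for any differences in baseline variables despite randomization". The same rule governs the binary secondary outcome: "Logistic regression will be used for attainment of post-stroke hypertension treatment goal of <130/80 controlling for any differences in baseline variables". No candidate variables, test or threshold are given.

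The data for a fixed adjustment set exist:

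- **Baseline SBP.** Section 6.1 states: "Patient will be asked to use this cuff to collect a baseline blood pressure measurement at the time of enrollment". The Data Collection Schedule lists "Blood pressure measure under direct observation" at week 0. Section 6.1 also takes a discharge-day reading from the health record, and no role in the analysis is stated for it.
- **Stratification factors.** Section 5.1 states: "Patients will be stratified according to network size (<5 vs 5 or more) and location of hospitalization (MGH or BWH"). Section 9 does not mention either factor.
- **Other baseline variables.** The Data Collection Schedule lists age, sex, stroke severity and a comorbidity index. Section 6.1 adds a depression score, and "Additional covariates, such as medication use, will be retrieved from the EHR".

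Section 9.2 sizes the trial on "Assuming a mean blood pressure of 150 +/- 13 points in the individual counselling arm", a 10 mm Hg difference, alpha 0.05 and 80% power, giving 54 patients. It does not say whether 13 is the SD of the SBP level or of its change, and it gives no correlation between baseline and week 12.

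**The concern.** In a randomised trial an observed baseline difference is chance. Adjustment gains precision when a variable predicts the outcome, whether or not the arms happen to differ on it. For an SBP outcome the obvious predictor is baseline SBP. The rule in 9.3 selects on the wrong property and leaves the selection open. It can be read in two ways:

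1. **Significance trigger.** Baseline SBP enters only when the arms differ by chance. At p<0.05 that is about 5% of trials.
2. **Literal.** Any difference counts, so every collected variable enters. At least eight are named: SBP, age, sex, stroke severity, comorbidity index, depression score, network size and medication use.

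Under either reading the final set can be decided once outcomes are known, and Sections 10.1 and 10.3 give the investigators standing access to de-identified study data. At stake are a pre-specified primary result and precision from data the trial already collects.

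**Working it through.** **Step 1: the plan's own figure.** Inputs from 9.2: difference 10, SD 13, alpha 0.05 (taken as two-sided), power 80%.

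n per arm = 2(1.960 + 0.842)² × 13² / 10² = 26.5, rounded up to 27, or 54 in total. This matches. It is an unadjusted two-sample calculation. Power at 27 per arm is 80.7% by the normal approximation and 79.2% by the t-test.

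**Step 2: inputs not in the documents (assumptions).** Correlation ρ between baseline and week 12: 0.2, 0.5, 0.7. Baseline SD: 13, with 10 and 16 as alternatives. Trigger: p<0.05, with 0.20 and 0.50 as alternatives.

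**Step 3: formulas.** With baseline SD s₀ and week-12 SD s₁:

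- SD of unadjusted change = √(s₀² + s₁² − 2ρs₀s₁)
- Residual SD with baseline SBP in the model = s₁√(1 − ρ²)

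At ρ = 0.2 / 0.5 / 0.7:

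- SD 13 at both visits: change SD 16.44 / 13.00 / 10.07; residual SD 12.74 / 11.26 / 9.28.
- 13 as the SD of change: level SD = 13/√(2(1 − ρ)) = 10.3 / 13.0 / 16.8; residual SD = 13√((1 + ρ)/2) = 10.07 / 11.26 / 11.99.

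**Step 4: power by simulation.** 27 per arm, true effect 10, 40,000 replicates, trigger p<0.05. Each cell shows baseline SBP always adjusted, then the trigger rule, in percent.

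| Reading | ρ = 0.2 | ρ = 0.5 | ρ = 0.7 |
|---|---|---|---|
| Change score, SD 13 at both visits | 80.0, 60.6 | 88.7, 80.1 | 96.9, 95.0 |
| Change score, 13 = SD of change | 94.2, 80.6 | 88.4, 79.9 | 84.6, 80.0 |
| Week-12 SBP as outcome, SD 13 | 80.3, 79.4 | 88.4, 80.0 | 97.1, 81.1 |

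The losses by subtraction are 19.4 / 8.6 / 1.9 points, 13.6 / 8.5 / 4.6 points and 0.9 / 8.4 / 16.0 points. The third row is a sensitivity case, because 9.3 defines the outcome as a reduction.

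**Step 5: sensitivity of the loss (ρ = 0.2 / 0.5 / 0.7).**

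- Change score, SD 13 at both visits: 16 / 7 / 1 points with trigger p<0.20; 10 / 4 / 0.7 with p<0.50.
- 13 as SD of change: 10 / 6.5 / 4 points with p<0.20; 5.5 / 4 / 2 with p<0.50.
- Change score, week-12 SD 13, trigger p<0.05: 10.6 / 2.2 / −0.1 points with baseline SD 10; 28.7 / 18.2 / 8.0 with baseline SD 16. The near-zero value arises because, with baseline SD 10 and ρ = 0.7, the change SD is √(100 + 169 − 182) = 9.33 against a residual SD of 9.28.

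**Step 6: literal reading.** SBP plus seven independent covariates, 27 per arm, 30,000 replicates. Power is 73.7 / 83.6 / 94.3% if the seven explain nothing further, and 82.8 / 90.4 / 97.7% if they explain 20% of the remaining variance. SBP alone gives about 80 / 89 / 97%. Entering everything can therefore cost or gain.

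**Step 7: type I error.** One fixed trigger gives about 2.5% to 5.0% over the settings tested. Taking the better of the adjusted and unadjusted p-values gives about 6% to 8% with one covariate.

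**The case against.** The strongest reply is that 9.3 is loose shorthand for baseline adjustment. It does not say that adjustment is made *only* for variables that differ, and on the literal reading baseline SBP always enters, so nothing is lost by omitting it. That stands as a limit: the power loss belongs to the trigger reading. It does not remove the point, because the shorthand still names no covariate and no threshold.

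A second reply is that this is a 60-patient pilot whose sample size is correctly computed. That also stands and limits the severity. The pilot nevertheless states an efficacy hypothesis with alpha and power.

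Three stronger inferences are tempting, and the documents do not support them:

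- **That the trial is underpowered as planned.** Power below 80% depends on the reading and on assumed values. In several cases the loss is only a gain not taken.
- **That type I error is inflated.** A single fixed trigger is conservative. The 6% to 8% figure requires choosing between results after seeing both, which the plan does not propose. It is not a ceiling either: with several candidate covariates the figure would be higher.
- **That the model could be a repeated-measures one**, because no noun follows the word linear and 9.1 says "rates of systolic blood pressure change at 3 months will be equal in the intervention arm". Section 9.3 fixes the outcome at 3 months, at the exit interview, and the parallel sentence names logistic regression. Linear regression is the natural reading.

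**Conclusion.** The point holds as a defect of specification with a better method readily available. Covariate choice depends on observed differences, without threshold or list, and no supplied text commits baseline SBP or the strata to the model.

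The cost is mainly forgone power, and its true size is unknown. With 27 per arm, a p<0.05 trigger and ρ from 0.2 to 0.7, it is about 2 to 19 points (change score, SD 13 at both visits) or about 5 to 14 points (13 as the SD of change). It shrinks with looser triggers. It is near 0 with baseline SD 10 and ρ = 0.7, and reaches about 29 points with baseline SD 16 and ρ = 0.2. Under the first of these readings with this trigger, power falls below the stated 80% when ρ is below about 0.5; that cut-off does not carry over to other baseline SDs. The cost of omitting the strata cannot be computed, because the documents do not say how much variance they explain.

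This should be fixed, but it does not undermine the stated sample size.

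**What to change.** Replace the adjustment rule in 9.3 with wording such as:

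> Change in SBP from baseline to week 12 will be analysed by linear regression on arm, baseline SBP (the directly observed week-0 study-cuff reading, not the discharge-day health-record reading), network-size stratum and hospital stratum, whatever the observed baseline balance. No covariate will be added or removed because of observed imbalance.

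With baseline SBP in the model, change and week-12 SBP give the same treatment effect, so the primary outcome is unaltered.

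The same edit must state how Spaulding patients are coded. Sections 3 and 5.1 give the hospital stratum only two levels, MGH and BWH, while Spaulding also enrols, so the hospital term cannot be built until this is settled.

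Apply the same principle to the secondary models. For the <130/80 goal, use arm, baseline blood pressure (the sponsor to name systolic, diastolic or both) and the strata, with a reduced set named in advance in case of non-convergence. For PROMIS, use arm and the strata.

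The cost is protocol and SAP wording; all terms are already collected. Adding the two strata to baseline SBP costs 0.1 to 0.3 power points at 27 per arm, assuming stratified blocks of 4 and no stratum effect (80.1 to 79.8%, 88.8 to 88.6% and 96.8 to 96.7% at ρ = 0.2, 0.5 and 0.7).

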Social networks could be leveraged to address hypertension control among post-stroke survivors for at least two reasons: 1) social networks influence and regulate the adoption of diet patterns, physical activity, and medication adherence, all of which are important to blood pressure management; 2) social network interventions relying on social support and social network education have been successful in blood pressure control in primary care settings.¹⁰

2. Specific Aims and Objectives

This proposed pilot project aims to leverage social networks to improve hypertension control for patients who have had an ischemic stroke. The study team hypothesizes that leveraging an individual's social network to monitor and treat blood pressure will be more effective than a standard intervention to control post-stroke blood pressure. This study has the following Specific Aims:

Aim 1: To determine the effects of a social network intervention versus individual hypertension counseling on blood pressure control for patients discharged after ischemic stroke. In a pilot study, the study team will randomize 60 patients with ischemic stroke to 1) individual teaching, and 2) a social network intervention. The primary outcome will be the absolute reduction in systolic blood pressure at 3 months.

Aim 2: To determine the shortest questionnaire that maximizes network information important for the intervention. We will test whether a subset of our social network questionnaire is sufficient for information used in the network intervention. For the same participant, we will compare intervention-relevant network metrics (network size, proportion of network members who have hypertension) derived from the short version versus full version.

[figure not shown]
Aim 3: To understand the acceptability, adoptability, and mechanisms of the social network intervention. The study will explicitly evaluate implementation of the intervention by collecting and evaluating quantitative and qualitative data directly from patients and their networks.

3. General Description of Study Design

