The study will enroll 60 patients hospitalized at Brigham and Women's Hospital, Massachusetts General Hospital and Spaulding Rehabilitation Hospital with a symptomatic and imaging-confirmed ischemic stroke and hypertension. During the index stroke admission, all enrolled patients' networks will be mapped using the validated PERSNET instrument.¹¹ Participants will then be stratified according to network size (<5 vs 5 or more) and location of hospitalization (MGH or BWH). Network size is the most potent network metric related to stroke recovery.⁹ Patients in both arms will be administered blood pressure medications as needed during the hospitalization. Patients will then be randomized to receive individual hypertension counseling (control) or the social network intervention. In the individual hypertension counseling arm, patient networks will not be acted upon. The index patient will meet via Zoom three times over the course of 3 months with a clinical research nurse for blood pressure education. In the social network arm, the results of the PERSNET instrument will be used to identify the most influential network members based on their network position, driving distance from the patient, speaking frequency, and whether they have high blood pressure. Network members will then be contacted and consented for participation in the study. The index patient and consented network members will meet via Zoom for three visits over 3 months with a clinical research nurse for blood pressure education and teamwork coaching. The primary outcome of the study will be the absolute reduction in systolic blood pressure at 3 months follow-up.

3.1 Study Schema:

Screen potential participants hospitalized at MGB by inclusion and exclusion criteria Total N: 60 patients

4. Subject Selection

4.1 INCLUSION/EXCLUSION CRITERIA:

4.1a Patient subjects

The study team will enroll 60 patients hospitalized at Brigham and Women's Hospital, Massachusetts General Hospital and Spaulding Rehabilitation Hospital with a symptomatic and imaging-confirmed ischemic stroke and hypertension.

Inclusion Criteria:

1. Acute ischemic stroke defined clinically with support from imaging if necessary
2. 21 years of age or older
3. History of hypertension or has been newly prescribed blood pressure medications during index admission
4. Within 14 days after stroke

Exclusion Criteria:

1. NIHSS > 21
2. Significant aphasia (Score>1 on the language section of the NIHSS)

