All network members will then be asked to leave the Zoom meeting, except for the primary caregiver (if applicable). The patient will collect a final blood pressure measurement under direct supervision of the study nurse, complete the PROMIS physical function scale, and remap their network with the PERSNET instrument to assess any changes that may have occurred as a result of the study. The primary caregiver network member will be asked to complete the caregiver burden scale which will be sent to them via a link in the Zoom chat or via text message.

Outcomes

The primary outcome of the study will be absolute reduction in systolic blood pressure at 3 months. Secondary outcomes will be attainment of a post-stroke hypertension treatment goal and patient-reported physical function. Feasibility measures will also be assessed throughout the intervention. End line caregiver burden will be measured in the social network arm compared to historical control data.

The intervention process evaluation conducted using semi-structured qualitative interviewing during the final session (Social Networks arm) will be analyzed using qualitative software to identify themes using a grounded theory approach. Once the data are analyzed, the investigators will review the findings to consolidate observations into a common set of themes.

Finally, a shortened version of the validated PERSNET utilizing only a subset of the initial questionnaire will be tested for predictive accuracy against the results of the full validated PERSNET scale.

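### Section 9.3 names only positive predictive value for Aim 2, which does not count members that a short PERSNET misses, so it cannot by itself show that the short form is sufficient

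*Combined protocol and SAP*

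**What the plan says.** Section 2 states Aim 2 as "To determine the shortest questionnaire that maximizes network information important for the intervention" and adds: "We will test whether a subset of our social network questionnaire is sufficient for information used in the network intervention". It also commits, within the same participant, to "compare intervention-relevant network metrics (network size, proportion of network members who have hypertension"), short version against full version.

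Section 3 describes a main use of that information. In the social network arm, "the results of the PERSNET instrument will be used to identify the most influential network members", based on network position, driving distance, speaking frequency and high blood pressure.

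The Outcomes paragraph at the end of Section 6.4 says that "a shortened version of the validated PERSNET utilizing only a subset of the initial questionnaire will be tested for predictive accuracy", with the full PERSNET results as comparator.

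Section 9.3 has two sentences on Aim 2. The first says the team will assess how a subset of PERSNET questions "predict the set of network members who were engaged in the intervention". The second is "We will calculate positive predictive value of the subset questions versus full network survey questions". Section 9.3 gives no sensitivity, does not define a positive, and does not mention the paired comparison from Section 2.

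**The concern.** Whether a shortened questionnaire is sufficient depends on what is lost when questions are removed. The main error to look for is a member whom the full form would have picked out and the short form does not. PPV looks only at the members the short form returns and asks how many are right. A member who is never returned does not enter the calculation.

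A short form could therefore report a high PPV while leaving out people the intervention would have wanted to recruit. If a later study adopted it on that evidence, the loss would go unnoticed. The consequence is limited to Aim 2: the blood pressure outcome, the sample size and safety do not depend on it.

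**Working it through.** The plan gives no sample size, precision target or threshold for Aim 2, so there is no Aim 2 figure to reproduce. The check uses definitions and illustrative counts. All member counts, PPV values and ratios below are assumptions, not estimates for this trial.

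**Definitions.** Let TP be the reference members returned by the short form, k the number the short form returns, and m the number in the reference. Then PPV = TP/k and sensitivity = TP/m, so sensitivity = PPV × k/m. The two are equal only when k = m.

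**Case 1: shortening only removes names.** Every short-form member is then also on the full list, so TP = k and PPV = k/k = 100%. With a full list of m = 10:

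| Returned (k) | PPV = k/k | Sensitivity = k/10 | Network size understated by |
|---|---|---|---|
| 8 | 100% | 80% | 2 |
| 5 | 100% | 50% | 5 |
| 3 | 100% | 30% | 7 |
| 1 | 100% | 10% | 9 |

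**Case 2: shortening removes attribute questions and members are then ranked.** Wrong picks are now possible and PPV can fall below 100%, but misses are still not counted. At PPV 90%:

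- k/m = 1.0: sensitivity 0.90 × 1.0 = 90% (no gap)
- k/m = 0.8: 0.90 × 0.8 = 72%
- k/m = 0.6: 0.90 × 0.6 = 54%
- k/m = 0.5: 0.90 × 0.5 = 45%

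**What the Section 2 comparison adds.** Suppose the full form lists 10 members, 4 of them hypertensive, and 3 are selected as influential. The short form returns 5, of whom 2 are hypertensive. Network size is understated by 5, which the paired comparison shows. The proportion with hypertension is 4/10 = 0.4 and 2/5 = 0.4, so no difference appears. Both results are the same whether the 5 include none of the 3 influential members (sensitivity 0/3 = 0%) or all of them (3/3 = 100%). The comparison detects lost members but does not say which ones were lost.

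**Reading the two Section 9.3 sentences together.** They could mean short-form PPV against full-form PPV for engaged members. With 3 engaged members, all on the full list of 10, the full form has PPV 3/10 = 30%. A short form returning 5 members that include 2 of the 3 has PPV 2/5 = 40%. It scores better although it has lost one engaged member (sensitivity 2/3 = 67%).

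**Patients available.** Section 3 says that all enrolled patients' "networks will be mapped using the validated PERSNET instrument", and the data collection schedule lists PERSNET at baseline in both arms. A full-PERSNET reference therefore exists for all 60 planned patients. Section 6.1 says control networks are not acted upon, so engaged members exist only among the 30 planned intervention patients (Section 6.6).

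**The case against.** The strongest reply is that the protocol already covers most of the harm. Section 2 promises a within-participant comparison of network size, and lost members reduce network size. That commitment does not lapse because Section 9.3 does not repeat it, and a reader who infers that the comparison has been abandoned goes further than the documents allow. This part of the reply stands: Section 9.3 needs only a cross-reference. It does not answer whether the influential members are retained.

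A reader might also infer that the reference standard is wholly open, because Section 9.3 mentions engaged members in one sentence and the full survey in the next. The documents do not support that. The PPV sentence itself names the full survey, and the Outcomes paragraph in Section 6.4 names the full PERSNET. The engaged-member sentence can be a separate question for the intervention arm. Nor does the mention of engaged members reduce the network-size comparison to 30 patients, since that comparison needs no engaged members and PERSNET is collected in both arms.

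Third, members are ranked, and if both forms took the same number of top-ranked members, PPV would equal sensitivity. That is true, but the plan does not say the number is fixed.

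Finally, this is a pilot, Aim 2 is outside the listed primary and secondary outcomes, and sensitivity could be computed afterwards from the same data. This limits the weight of the point. Still, the questionnaire comparison is one of three stated aims, and its measure is better fixed in advance.

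**Conclusion.** The point holds for the choice of statistic. PPV alone cannot establish that a short PERSNET is sufficient, because missed members do not affect it. Against the full member list it is 100% by construction if shortening only removes names. If shortening instead changes the ranking, the gap between PPV and sensitivity depends on k/m, which the documents do not give. Over the assumed range of 1.0 to 0.5, a PPV of 90% corresponds to sensitivity from 90% down to 45%. The size of the gap in this trial is unknown, and it is zero if both forms select equal numbers.

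The conclusion rests on the definition of PPV and on Section 9.3 naming no other Aim 2 statistic. The paired comparison and the reference need only clearer wording. The change is worth making because it costs little.

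**What to change.** In Section 9.3:

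1. Define a positive as a member selected as influential from the full PERSNET, and state how many members each form selects or by what rule.
2. Report sensitivity beside PPV against that reference in all 60 planned patients. Both are needed, since a form that returns everyone has perfect sensitivity.
3. Give intervals that allow for clustering of members within patients, for example by resampling whole patients.
4. Keep prediction of engaged members as a separate analysis in the intervention arm, also with sensitivity.
5. Cross-reference the paired comparison of network size and proportion with hypertension in Section 2, and name the method.

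The cost is a few sentences and a little more analysis, including applying the selection rule to control-arm networks on paper only. The full PERSNET is already collected at baseline in both arms, so visits, procedures and sample size do not change.
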